#### **Exclusion criteria:**

1. Pregnant, potentially pregnant or lactating females. To satisfy radiation protocol, each female subject will be asked if she is pregnant, or possibly could be pregnant. A pregnant person will not be allowed to participate in the study. To ensure this, a pregnancy test will be administered to any female participants of child bearing age who have not had a hysterectomy.
2. Subjects without the required type of knee implant.
3. Subjects who are unable to perform stepping up and deep knee bend.
4. Subjects who are unwilling to sign Informed Consent/HIPAA documents.
5. Subjects who do not speak English and/or French.

### **Recruitment**

[name] will recommend eligible subjects for recruitment that have been implanted with the Zimmer Persona PS TKA whose post-operative conditions permit them to capably perform the study activities. Drs. [name] and [name] will be responsible for reviewing those subjects' medical records to determine if they meet the remaining eligibility required for the study according to the study-specific criteria. A Request for Partial Waiver of HIPAA Authorization for the purposes of recruitment will be submitted.

During review of medical files, Drs. [name] and [name] will ensure that each potential subject meets all eligibility requirements prior to being contacted about participation in the study. If patients meet all eligibility criteria, then Drs. [name] or [name] will contact the patients to explain the study, using the included script, and inquire as to whether or not they are interested in participating; If a subject is agreeable to participate, Drs. [name] or [name] will schedule a time for the patient to visit the Institute for Locomotion on the day of data collection. On this scheduled day, UT researchers will travel to the Institute for Locomotion to collect the kinematic data of participant implanted knees at least six months post-operatively under fluoroscopic surveillance using a C-arm fluoroscopic unit while subjects perform the following activities: stepping up and a deep knee bend. The fluoroscopic images will be stored on videotape and/or external hard drive for subsequent analysis.

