## ***Hypothesis:***

1. It is hypothesized that subjects having a PS TKA will experience greater posterior femoral rollback, axial rotation and weight-bearing flexion than subjects having a PCR TKA.
2. It is hypothesized that subjects having a Persona TKA will experience better kinematic patterns than subjects previously analyzed having a NexGen TKA.

***Study design:*** In vivo knee kinematics will be assessed for 25 subjects that have been implanted with a Zimmer-Biomet Persona fixed bearing posterior stabilizing (PS) total knee arthroplasty (TKA) by [name] [name] of the Institute for Locomotion, Aix-Marseille University, Hopital Sainte-Marguerite. The other 25 subjects with the Zimmer-Biomet Persona fixed bearing poster cruciate retaining (PCR) TKA will be provided by another surgeon at a separate site, which has yet to be determined. [name] and [name] both of the Institute for Locomotion, Aix-Marseille University, Hopital Sainte-Marguerite will serve as Sub-Investigators. [name] of the University of Tennessee will also serve as a Sub-Investigator. Enrollment will be increased to 28 subjects per implant type to ensure that researchers acquire the necessary 25 usable datasets for analysis for each implant type and also

to account for any subjects that may drop out of the study. All TKAs should be judged clinically successful (KSS > 75). Each subject should have a well-functioning prosthesis, be at least six months post-operative, and should have good-to-excellent post-operative passive flexion.

Deciding which subjects received which kind of implant was up to the discretion of the study surgeon, according to his professional opinion. The determination as to which type of implant subjects received is outside the scope of this particular study. Subjects will already have the knee implants and must be at least six months post-operative.

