#### ***Inclusion and exclusion criteria:***

We will use the following inclusion criteria to recruit participants for this study:

1. Subjects will have a Zimmer Persona fixed bearing PS TKA.
2. Subjects must be at least six months post-operative.
3. Subjects will have KSS greater than 75.
4. Participants must be able to perform the required activities - stepping up and a deep knee bend.
5. Subjects must be willing to sign the Informed Consent (IC) / HIPAA form to participate in the study.
6. Bilateral subjects may be included in the subject population.

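### PS patients enter by one individual's recommendation and PCR patients by an undescribed route, so differing selection cannot be told apart from an implant difference

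*Protocol*

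**What the plan says.** **PS arm.** The study design (Protocol, under Hypothesis) takes 25 PS subjects from one surgeon at one institute. The Recruitment section describes how they enter. A named individual, whose name is removed from the public text, "will recommend eligible subjects for recruitment that have been implanted with the Zimmer Persona PS TKA whose post-operative conditions permit them to capably perform" what is asked of them. Other physicians then check the records of the recommended subjects for the remaining eligibility and contact those who qualify.

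**PCR arm.** The other 25 subjects "will be provided by another surgeon at a separate site, which has yet to be determined". The protocol does not say how that surgeon will choose them, and item 1 of the inclusion list names only the PS implant.

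**Criteria.** Item 4 of the inclusion list reads "Participants must be able to perform the required activities - stepping up and a deep knee bend", with no test or threshold. KSS above 75 and at least six months since surgery are required. The study design adds that subjects should have a well-functioning prosthesis and "should have good-to-excellent post-operative passive flexion", without a cut-off.

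**Allocation and analysis.** Implant choice was at the surgeon's discretion, and "The determination as to which type of implant subjects received is outside the scope of this particular study". Hypothesis 1 compares rollback, axial rotation and weight-bearing flexion between PS and PCR. The SAP (Data Analysis) plans a t-test, Welch test or Mann-Whitney test for continuous variables and Fisher's exact test for lift-off. None of these has a covariate, surgeon or site term.

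**The concern.** The recommendation is the only way into the PS arm, and it turns on a judgement about performing the two tasks from which the outcomes are measured. Maximum weight-bearing flexion is the end point of the deep knee bend itself. An eligible patient who is never recommended is never reviewed, and no record of the omission is kept.

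Selection of this kind would matter less for the PS-PCR contrast if it worked identically in both arms. Nothing in the plan makes it do so: the PCR arm comes from a different surgeon and site, with no common rule for who is put forward. If one source is more selective than the other, the arm means differ for that reason alone, and the unadjusted tests attribute the gap to the implant. A larger sample would not help, because the bias does not shrink with n.

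**Working it through.** The plan gives no figure for selection, effect size, SD or power, so there is nothing of its own to reproduce. The check has two parts.

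**1. Does any step equalise selection between the arms?**

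| Step | PS | PCR |
|---|---|---|
| Who puts patients forward | One named individual | Another surgeon |
| Stated basis | Able to perform the activities | Not stated |
| Record review | Of recommended subjects only | Not described |
| Consecutive invitation | None described | None described |
| Log of those not put forward | None described | None described |
| Adjustment in the analysis | None | None |

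KSS, time since surgery and the record review set a floor. They do not govern which patients above the floor are invited.

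**2. How large could the effect be?** This is an illustration.

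From the documents: 25 usable datasets per arm and alpha 0.05. Assumed, because the documents give no value:
- the test is two-sided (the SAP does not state sidedness);
- the implant has no true effect;
- the correlation rho between the recommender's impression and the outcome is 0.3 to 0.5;
- the fraction f of eligible patients put forward is as shown below.

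If the top fraction f on a normally distributed impression is put forward, the outcome mean shifts by

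shift = rho × φ(z_f) / f, in SD units,

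where φ is the standard normal density and z_f the cut-off that leaves fraction f above it.

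- f = 0.50: φ/f = 0.3989/0.50 = 0.798. The shift is 0.3 × 0.798 = 0.239, or 0.5 × 0.798 = 0.399.
- f = 0.75: φ/f = 0.3178/0.75 = 0.424. The shift is 0.3 × 0.424 = 0.127, or 0.5 × 0.424 = 0.212.

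The chance of a significant result comes from the noncentral t with 25 + 25 − 2 = 48 df, noncentrality = shift × √(25/2) = shift × 3.536, and critical value 2.011.

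| Scenario | rho | Net shift (SD) | Noncentrality | Rejection |
|---|---|---|---|---|
| Selection equal in both arms | any | 0 | 0 | 5.0% |
| Best 50% in one arm, no selection in the other | 0.3 | 0.239 | 0.846 | 13.2% |
| Same | 0.5 | 0.399 | 1.410 | 28.2% |
| Best 50% against best 75% | 0.3 | 0.239 − 0.127 = 0.112 | 0.397 | 6.8% |
| Same | 0.5 | 0.399 − 0.212 = 0.187 | 0.661 | 9.9% |

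For scale, 25 per arm gives 80% power for a true difference of about 0.81 SD. The one-sided scenario at rho 0.5 is therefore about half of that (0.399/0.81 = 0.49).

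**The case against.** The strongest reply is that the Recruitment text describes a pre-screen, not a ranking. It speaks of eligible subjects who can do the tasks, which is close to inclusion item 4. Item 4 has no test or threshold, so someone who knows the patient has to judge ability before contact, and a consecutive list would need the same judgement. The study also deliberately targets successful knees, and that narrows the room for differential selection. This stands in part: the ability judgement is needed and should stay. It does not explain why that judgement should decide who is listed at all, unlogged and by a different person in each arm.

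A reader might infer that both surgeons choose their best performers and so manufacture an implant effect. The documents do not support that. The recommender's role is not given in the Recruitment section. That this is the implanting surgeon is probable from the study design and from the consent section, where a named individual stays away to avoid coercion, but it is an inference. For the PCR arm no procedure is described, so selection on function there is a possibility and not a stated practice.

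A reader might also infer that adjustment is useless. That is too strong. The protocol collects range of motion, KSS, BMI, time since surgery and other conditions, and these are plausible proxies for an impression of function. Adjusting for them could remove part of the bias, but the SAP does not plan it.

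Finally, the statement that implant choice is out of scope concerns who received which implant. It does not cover who, among patients already implanted, is invited, and that is under the study's control.

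**Conclusion.** The concern holds in this form: the plan has no common, recorded rule for putting eligible patients forward in the two arms, so a difference in selectivity cannot be distinguished from an implant difference in the planned tests. Existing gates limit the problem without removing it. Whether such a bias would occur, how large it would be and which way it would run cannot be determined from the documents; it could mask a real difference as easily as suggest one.

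The rejection rates of 13 to 28% (selection in one arm only) and about 7 to 10% (best half against best three quarters) rest wholly on the assumed correlation and fractions. They show plausible scale and are not estimates for this study. The lower range is the fairer guide if both sources select to some degree. The change is worth making before enrolment, because unrecorded selection cannot be reconstructed afterwards.

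**What to change.** At both sites, have the sub-investigators who already review records (or their equivalents at the second site) list from the implant log all patients with the relevant Persona implant who are at least six months post-operative. Apply the same written criteria to everyone listed, including the ability judgement, and invite eligible patients consecutively by surgery date until 28 per arm are enrolled. Log those ineligible, not invited or declining, with reasons, and report the log by arm. Because the second site is not yet chosen, the rule can be set there from the start.

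The cost is a change of protocol wording, modest extra record screening and possibly slower enrolment.

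This does not remove the larger confounding. Implant coincides with surgeon and site, so no surgeon or site term can separate them. State that as a limit on the conclusion for Hypothesis 1.

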### **Data Collection**

On the day the fluoroscopic procedures will take place, researchers selected by [name], student research assistants ([name], [name], [name], [name]) with the Center for Musculoskeletal Research (CMR) will travel to the Institute for Locomotion to collect the data. A study Investigator will be present for the fluoroscopy procedures. Drs. [name] or [name] will consent the participants. They will meet with each potential participant individually to make sure s/he has been properly informed of the procedures and to help with any of the IC/HIPAA form. Subjects will be informed that they do not have to participate and are free to leave if they wish and will answer any questions subjects may have about the study. Participation is entirely voluntary.

After consent has been obtained and eligibility has been confirmed, a study physician will administer the New Knee Society Score survey to all participants.

In addition to fluoroscopy video, subjects will be videotaped from the shoulders down (to maintain subject anonymity) while performing the activities (live feed perspective). During the fluoroscopy procedure, the radiation technician (RT) will follow the motion of the implanted knee with the fluoroscopy machine; only the knee joint (from the fluoroscopy machine) will be

recorded on the fluoroscopy footage. The practice portion of the data collection without radiation will not be video-recorded. The participant will be allowed to rest as necessary and be instructed to stop the activity at the first sign of pain. The speed level of each trial will be based on the comfort level of the subject. One of the researchers will be ready and in close proximity to assist each subject in case the participant requires help. This precaution will be practiced for all participants, regardless of physical wellbeing, age or prior results; no assumptions will be made as to any participant's capabilities.

Multiple trials of each activity may be conducted to ensure usable images have been acquired to complete the study. Radiation time will be kept as low as reasonably achievable (ALARA) and will not exceed two minutes. The RT will start the fluoroscope just prior to the subject beginning each activity trial and will stop the fluoroscope immediately after the subject completes each activity trial to ensure that the subject is not exposed during idol periods. Fluoroscopy on-time will be recorded on each subject's IC.

When both the subject and study team are ready, the following activities will be performed:

1. Step up
  - a) The subject will begin standing at rest with his/her knee in question slightly forward in front of a small set of portable stairs.
  - b) The subject will then begin to ascend the stair case beginning with her/his lead foot, making sure that with each step, the foot is landing one step above the other.
2. Deep knee bend
  - a) The subject will begin standing in a starting position in which the knee is fully extended. When ready the subject will flex the knee through its full weight bearing range of motion. Once maximum weight bearing flexion is achieved the activity is complete, and the subject can rise to a comfortable resting position.

The fluoroscopic footage for these activities will be stored on digital video files on a secure computer workstation, and participant information will be removed and replaced with identifiers by researchers selected by [name] to lead the study, which may include any researchers that attend data collection. All researchers with access to identifiable subject data will sign statements of confidentiality. This study data will then be uploaded onto a secure server that University of Tennessee researchers will use to conduct the kinematic analysis using a 3D-to-2D image registration technique the allows researchers to determine the 3D kinematics of the tibio-femoral joint for each of the frames in question. Once each of the frames has been analyzed for a single participant, kinematic curves can be produced to describe the motions of the joint. It is not feasible for a participant to be identified merely by the components within their individual implants.

### **Private Health Information/Medical Record Data**

The surgeon and his staff will provide subjects' clinical information from their medical records – PHI – to [name] and his researchers to aid in the interpretation of the results and correlate clinical outcomes versus kinematic results, although only researchers present during data collection or those appointed by [name] to lead the study will have access to PHI; they will sign confidentiality statements. This information can be used to rule out any unique

kinematic patterns. This information will only be used by the UT researchers and will not be provided to any other source.

The clinical/demographic information acquired from the medical records with participant authorization obtained as required by HIPAA will include:

- the range-of-motion (at least 6 months post-operative),
- DOB, body weight, Body Mass Index (BMI),
- date of surgery,
- Subjects post-operative KSS (must be >75),
- previous medical assessments that are not a part of this particular research study, that may alter the kinematic results, such as previous knee x-rays,
- post-operative time and any other conditions that may alter the kinematic results, such as back problems, ankle fusion, or contra-lateral knee problems.

The surgeon's office will also relate the implant component information and surgical technique details:

- Size of: femur, tibial plate, articular surface thickness [mm], patella
- Product/Reference # of: femur, tibial plate, polyethylene (PE) insert, patella
- Lot # of: femur, tibial plate, PE insert, patella
- Surgical operation notes
- Use (if any) and details of intraoperative surgical technologies, such as robotic assistance, subject-specific cutting guides, surgical navigation, etc.

The subject data – fluoroscopy frames, video footage and data from medical files – will be uploaded and stored on CMR's secure server for use in this and future studies (if participant permission is obtained via IC) by the researcher(s) who attend data collection or appointed by [name]. Once data has been uploaded, the database automatically removes subject identifiers and assigns an ID for each subject. Only these files of de-identified data (no dates of birth or surgery) are now available for researchers to review and analyze. Only [name] (Sub-I) has access to the identifiable data that was originally uploaded by the GRA, as it remains in a password-protected portion of the secure server. Only [name] can grant access to this identifiable password-protected portion of the database by changing a user's level of authentication with different privilege levels. Researchers would like to retain this study data in our secure database so as to continue to add relevant, current data to our digital collection to help us work with manufacturers in the future to create better implants that last longer and will not require revision surgery. Participants will be asked if their study data may remain a part of the CMR data collection for use in future studies in the IC. Likewise, should a subject choose to withdraw from the study, s/he will have the option as to whether or not data collected from them at the point of withdrawal may be used for data analysis or if their information should be destroyed from CMR records; subjects choosing to withdraw will be asked to complete a Revocation of Consent wherein they may indicate their preference regarding the data collected from them.

On the day of data collection, the list of subject names will be given to UT researchers and the researchers will use this to generate subject-specific identifiers. A table will be generated for this study, indicating the participant's name and generated ID number; this table with subject names

and corresponding ID numbers will be provided to the surgeons' staff, so the staff will be aware of which identifier is linked with each subject. Then, study staff will upload the PHI from medical files into an excel spreadsheet created by the UT researchers present during data collection or those appointed by [name] (who will sign statements of confidentiality) that will only have the generated ID numbers. This spreadsheet will be securely transferred to UT researchers via UT's secure email known as the Vault. See 'Computer Database' section under Participant Confidentiality for additional details regarding the actual acquisition of PHI data from the surgeon's office.

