## DATA ANALYSIS

Once the subjects have completed the activity, the fluoroscopic videos will be stored digitally and specific frames of interest will be captured from the video and exported into the preprocessing software. The specific frames of interest will be full extension, maximum knee flexion (both inclusive), and 30° knee flexion increments during the complete flexion cycle.

Our 3D to 2D registration technique will be used to overlay the 3D models of the implanted components on their projection in the 2D fluoroscopic image. The fluoroscopic video would be digitized into frames and corrected for distortion. From here, the distortion-free images would be used with the 3D to 2D registration technique to extract in vivo patient femorotibial kinematics, which involves overlaying the 3D models of the components on their projection in the 2D fluoroscopic image.

Statistical analysis of the data will be carried out to analyze the two cohorts. All variables, except for lift-off and VAG, will be denoted as continuous. The data will be first checked for normality using the Shapiro-Wilk test. Only when the data is found to be normally distributed will parametric tests be used; otherwise, non-parametric tests will be used. The data will also be tested for equality of variance using the Barlett's test and Levene's test. The final selection criterion for the type of test to conduct will be based on the check for normality, as well as the check for equal variance. Therefore, for all the continuous variables, the following tests will be used:

1. Student's t-test (when the data is normally distributed and has equal variance).
2. Welch Anova test (when the data is normally distributed but has unequal variance).
3. Wilcoxon Mann Whitney U-test (when the data is not normally distributed).

Lift-off, as applicable, will be treated as a categorical variable in this study and a contingency analysis using the Fisher's exact test will be carried out. All statistical tests will be carried out at 95% confidence level ( $\alpha=0.05$ ) and will be performed using JMP® Statistical Discovery™ (SAS Institute Inc., Cary, NC) software.

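### Time since surgery is not aligned between the PS and PCR cohorts and is not in the SAP's tests, so a follow-up imbalance may appear as an implant difference

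*Protocol*

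**What the plan says.** **Eligibility.** The protocol's inclusion criteria set a floor: "Subjects must be at least six months post-operative". The study design text under Hypothesis repeats it: "Subjects will already have the knee implants and must be at least six months post-operative". Recruitment uses the same floor. None of these sections gives a ceiling, a window or a matching rule.

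**Source of the cohorts.** The PS subjects come from one surgeon's practice. The PCR subjects "will be provided by another surgeon at a separate site, which has yet to be determined". Implant choice was made by the surgeon before the study and was not randomised.

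**Data collected.** The medical-record section lists "date of surgery" and, as a separate item, "post-operative time and any other conditions that may alter the kinematic results". The stated purpose of the record data is "to aid in the interpretation of the results and correlate clinical outcomes versus kinematic results". On the files given to analysts, the same section says: "Only these files of de-identified data (no dates of birth or surgery) are now available for researchers to review and analyze".

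**Analysis.** The SAP's Data Analysis section offers three routes for continuous variables: "Student's t-test (when the data is normally distributed and has equal variance"), a Welch test, or a Mann-Whitney test. Lift-off goes to Fisher's exact test. The SAP names no covariate, stratification, matching or between-cohort comparison of follow-up time.

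**The concern.** Each knee is imaged in one session, at whatever time after surgery the subject happens to have reached. Two surgeons can both comply with the protocol while one offers mostly recent operations and the other mostly older ones. If follow-up time affects rollback, axial rotation or weight-bearing flexion, as the protocol's own list allows, that difference enters the Hypothesis 1 comparison in full and in either direction. A two-sample test has no means of separating it from the implant.

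Unlike surgeon and site, time since surgery varies within each cohort. It is therefore a source of bias that design can limit and analysis can partly remove.

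**Working it through.** **Inputs from the documents.** 25 usable datasets per implant type (Protocol, study design); α = 0.05 (SAP). Sidedness is not stated, so two-sided tests are assumed. The documents give no SD, no effect size and no relation between follow-up time and kinematics, so there is no figure of the plan's own to reproduce on this point.

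**Step 1: effect of an assumed shift in flexion.** Suppose there is no true implant effect and follow-up time alone moves mean weight-bearing flexion in favour of PS.

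- SE of the difference = SD × √(2/25).
- SD 15 degrees (assumed): 15 × 0.2828 = 4.24 degrees.
- SD 20 degrees (assumed): 20 × 0.2828 = 5.66 degrees.
- The probability of a significant result favouring PS is the upper tail of the noncentral t distribution with 48 df and noncentrality shift/SE, beyond the two-sided 5% critical value.

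| Assumed shift (degrees) | SD 15 | SD 20 |
|---|---|---|
| 0 | 2.5% | 2.5% |
| 2 | 6.7% | 5.3% |
| 4 | 15.0% | 10.3% |
| 6 | 28.3% | 17.9% |
| 8 | 45.5% | 28.3% |

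**Step 2: the same mechanism without units.** Let r be the within-cohort correlation between time and outcome, and D the difference in mean time in within-cohort SDs. The false shift is r × D outcome SDs. Two-sided rejection rates with no implant effect (nominal 5%):

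- r = 0.2, D = 1: shift 0.2 SD, 10.7%.
- r = 0.3, D = 1: shift 0.3 SD, 18.0%.
- r = 0.3, D = 2: shift 0.6 SD, 54.7%.
- r = 0 or D = 0: 5.0%.

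In simulations of 20,000 studies per setting, a linear model with time as covariate brought the rate back to 4.8% to 5.3%, with mean bias near zero. The simulated relation was linear, so this is the favourable case for adjustment.

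**Step 3: the price of adjustment.** The variance of the adjusted cohort difference is multiplied by about 1 + D²/4.

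- D = 1: 1 + 1/4 = 1.25.
- D = 2: 1 + 4/4 = 2.

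For a true effect of 0.8 SD, with time unrelated to the outcome, power is about 79% at D = 0, 70% at D = 1 and 50% at D = 2.

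**Step 4: where adjustment fails.** Suppose one cohort were seen at 6 to 9 months and the other at 24 to 48 months, spread evenly on the log scale. Both would comply with the protocol.

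- Difference in mean log months: ½ ln(24 × 48) − ½ ln(6 × 9) = 3.52 − 1.99 = 1.53.
- Within-cohort SDs: ln(9/6)/√12 = 0.117 and ln(48/24)/√12 = 0.200; pooled 0.164.
- D = 1.53/0.164 ≈ 9.3, and the variance factor is 1 + 9.3²/4 ≈ 23.

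The two ranges do not overlap, so an adjusted difference would be extrapolation. Only recruitment can deal with that case.

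**The case against.** **The subjects are selected as recovered.** The study design requires a KSS above 75, a well-functioning prosthesis and good-to-excellent passive flexion. This probably narrows differences in stage of recovery. But these are entry thresholds: they do not equalise rollback, rotation or weight-bearing flexion among those who pass, and the protocol still lists post-operative time as relevant.

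**The protocol does not ignore the variable.** A reader might infer that it does. The documents do not support that: the variable is collected and is meant to help interpretation. What is missing is a prespecified use of it. Without one, any later adjustment is open to selective reporting, and it may be impossible if the analysts' files lack the information.

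**The size is assumed.** This stands. The SDs, shifts and correlations above are illustrations, and only flexion is given in its own units. A reader might infer that the planned tests would declare a follow-up difference significant. Even the largest shift shown does so in fewer than half of studies, so the word is may.

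**Implant is aliased with surgeon and site anyway.** This also stands, and it limits what any adjusted estimate can mean. It is not a reason to leave in a bias that can be reduced.

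**Adjustment costs power.** True, and materially so when imbalance is large. That favours matching at recruitment over reliance on the model alone.

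**Conclusion.** The gap is plain in the text: a six-month floor, no ceiling, no alignment between two cohorts from different sites, and no use of follow-up time in the tests. A bias in the Hypothesis 1 comparison follows only if follow-up differs between cohorts and is also related to the outcome. The documents quantify neither, so the bias is possible rather than shown. With 25 per cohort and the assumed SDs of 15 to 20 degrees and shifts of 2 to 8 degrees, the chance of a false PS advantage is about 5% to 46% instead of 2.5%.

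A reader might also infer that adjusting for time would yield the effect of the implant. It would not. It removes the time component where follow-up ranges overlap, and what remains is still a difference between surgeons and sites as well as implants.

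**What to change.** 1. **Recruitment.** In the protocol's study design, state that PCR subjects will be recruited within the post-operative time range seen in the PS cohort, frequency-matched in two or three time bands. Carry this into PCR eligibility criteria, which have to be added because the current inclusion list admits only PS knees. On the text, the PCR site is not yet chosen, so this can still be arranged.
2. **Data file.** Keep months since surgery and age as derived numbers in the de-identified analysis file, since dates of surgery and birth are withheld from analysts.
3. **SAP.** Report time since surgery by cohort. For rollback, axial rotation and weight-bearing flexion, give the cohort difference with its 95% CI from a linear model with time since surgery (for example log months), plus age and BMI, alongside the unadjusted test. Use robust or rank-based inference if residuals are non-normal. Interpret the adjusted estimate only where follow-up ranges overlap.
4. **Interpretation.** State that implant remains fully confounded with surgeon and site, so the adjusted difference is not a pure implant effect.

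**Cost.** A few sentences in each document, two derived variables and no new measurements. The PCR recruitment pool becomes narrower. Precision falls as imbalance grows (variance about 1.25 times at 1 SD and 2 times at 2 SD), and the matching in item 1 limits this loss.
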